**SCHEDULE OF EVENTS**

	Screening	Treatment (Study Day 1)	Follow-Up (Study Day 2-3) 	Follow-Up (Study Day 4-7) 
Informed consent	X			
Inclusion/exclusion criteria	X			
Demographics	X			
Medical and surgical history	X			
ECOG Performance Status	X			
Confirmed presence of refractory CINV	X			
Serum pregnancy test 	X			
Physical exam with vitals, weight 	X		per routine frequency	
Complete metabolic profile 	X		per routine frequency	
Complete blood count with differential, platelets 			per routine frequency	
EKG QTc evaluation	X 		X 	
Patient CINV risk factors		X		X
Akynzeo® dispensing and administration		X		
Patient medication diary		X		
Collect hospitalization and emergency room visit data		X	X	X
Concomitant medications	X	X	X	X
Adverse event monitoring		X	X	X
MASCC Antiemesis Tool  (MAT)	X	X	X	X
Functional Living Index for Emesis (FLIE) scale 	X	X		X 
Patient preference Likert-scale				X 

 Women of childbearing potential only

 Subjects will be monitored for a total of 6 days following Akynzeo® dosing

 QTc evaluation on Day 3±3 days with single EKG. If patient experiences worsening cardiac symptoms during the study, additional EKG(s) will be performed as clinically indicated

 Complete on Day 5 only

 Daily unless otherwise indicated. Daily safety assessment and hospitalization/ER visit information on Days 2-7 may occur via in-person visit or telephone call from a study team member. Subjects will also receive a daily reminder (via in-person visit or telephone call) to complete required questionnaires/diaries.

 Complete on Day 7 only

 EKG, laboratory and physical exam results obtained within 4 weeks prior to the informed consent date may be used to fulfill study requirements. EKG results may be obtained after screening processes yield positive refractory CINV.

 To be completed daily for 4 days after CINV prophylaxis or Akynzeo® dosing.

 To be completed on the 5th day after CINV prophylaxis or Akynzeo® dosing

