### **2.1 Primary**

To determine the feasibility of using a fixed dose combination of netupitant and palonosetron (Akynzeo®) in the treatment of refractory CINV. For this study, refractory CINV is defined as nausea and/or vomiting that occurs after the first cycle of cancer targeted therapy despite guideline-based prophylaxis and after first-line rescue medication with either a dopamine receptor antagonist, steroid, and/or benzodiazepine.

Hypothesis: Feasibility, defined as more than 70% of selected study subjects completing all study related procedures, will be achieved.

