### **2.2 Secondary:**

- To evaluate the occurrence of adverse events using the National Cancer Institute Common Terminology Criteria for Adverse Events (CTCAE) version 4.03.10
- To evaluate complete response defined as no emesis and no use of rescue medication for 5 days after Akynzeo® administration.
- To characterize 24-hour CINV using a modified MASCC Antiemesis Tool (MAT). (**Appendix 1**)
- To evaluate 5-day health related quality of life recall using the Functional Living Index for Emesis (FLIE) scale.
- To evaluate healthcare resource utilization as defined by the number of emergency room visits, hospitalizations, and infusion center visits encounters regarding signs/symptoms associated with CINV over the seven-day study period.
- To evaluate the occurrence of refractory CINV using CINV risk assessment at follow up day 7 compared to treatment day 1.

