#### **3.1 Inclusion Criteria**

1. Adults greater than or equal to 18 years old.
2. Must have a histologically confirmed cancer diagnosis.
3. Must have refractory CINV defined as nausea and/or vomiting that occurs after the first cycle of cancer targeted therapy despite guideline-based prophylaxis and after first-line rescue medication with either a dopamine receptor antagonist, steroid, and/or benzodiazepine.
4. Eastern Cooperative Oncology Group (ECOG) performance status less than or equal to 2.
5. Life expectancy greater than 3 months.
6. Corrected serum calcium level less than or equal to 10.5 mg/dL.
7. Women of child-bearing potential must agree to use adequate contraception (hormonal or barrier method of birth control; abstinence) prior to study entry, for the duration of study participation, and for 14 days following completion of therapy.  
A woman of child-bearing potential is any female (regardless of sexual orientation, having undergone a tubal ligation, or remaining celibate by choice) who meets the following criteria:
  - a. Has not undergone a hysterectomy or bilateral oophorectomy; or
  - b. Has not been naturally postmenopausal for at least 12 consecutive months (i.e., has not had menses at any time in the preceding 12 consecutive months)
8. Women of child-bearing potential must have a negative pregnancy test prior to initiating study treatment.
9. Ability to understand and willingness to sign a written informed consent.

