### **5.1 Patient CINV Risk Factors**

Classifying CINV risk by chemotherapy type has provided a valuable framework for the development of international prophylactic antiemetic guidelines. However, considerable work has revealed a number of patient specific variables that may contribute to emetic risk. Therefore, antiemetic guidelines relying solely on emetogenicity of chemotherapy may potentially undertreat patients at higher individual emetic risk than what the chemotherapy alone suggests. CINV patient-related risk prediction models have been developed. Based on data from these models, several key patient risk factors will be collected on Study Day 1 prior to Akynzeo® dosing including: age, sex, alcohol consumption, history and severity of previous CINV, history of morning sickness with pregnancy, history of motion sickness, less sleep the night before chemotherapy, and pre-chemotherapy anxiety.

During the post-treatment observation portion of the study, subjects will receive a daily phone call from a member of the study team to inquire about any adverse event that the subject may

be experiencing and whether they have had any hospitalizations or emergency room visits since the last contact. During these calls, the study team member will also remind the subject to complete the MASCC Antiemesis Tool and medication diary. On Study Day 5 only, the subject will also be instructed to complete the FLIE scale. The subject will be asked to return to clinic on Study Day 3 (+3 days) for a single EKG. Additional clinic visits, physical exams, or laboratory tests performed during the 7-day treatment and follow-up periods will be scheduled according to routine care and according to the subject's treating physician.

Subjects will be asked to return all completed and unused study materials, including subject diaries and questionnaires to a member of the study team at their next routine clinic visit.

A more detailed description of selected assessments is included in the Efficacy Measures and Safety Measures sections.

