## 5.3 Future Directions

If feasibility is achieved on this study, then future plans would include analysis of secondary and exploratory objectives to determine if there are any trends towards a clinically-meaningful and plausible study endpoint, which would be further developed in a larger Phase II study. We have several key palliative care oncology collaborators, and ultimately plan to propose the Phase II concept through a cooperative group such as the [Palliative Care Research Cooperative Group](#) or the [Alliance in Clinical Oncology Trials](#) Symptom Intervention Committee, both of which [name] is an active member.

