## **5.5 Efficacy Measures:**

### **5.5.1 Patient Medication Diary**

Subjects will be asked to record all oral and self-administered medications received while on study. This will include any rescue medications used to treat their CINV each day, as well as any vitamins, homeopathic/herbal remedies, nutritional supplements, over-the-counter analgesic medication use, and all other over-the-counter "as needed" medications. Subjects will complete this diary (Appendix 3) on the day of Akynzeo® treatment (Study Day 1) and daily during the post-treatment observation portion of the study (Study Days 2-7).

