- (6) The occurrence of refractory CINV will be analyzed using CINV risk assessment at follow up day 7 compared to treatment day 1.

Patient demographic characteristics (age, sex, and patient reported race/ethnicity) will be described using standard descriptive statistics (n/% or mean/SD).

As an exploratory aim, regression analysis will be used to develop a predictive model for CINV, based on age, sex, history of >1 alcoholic beverage per day, history of motion sickness, history of hyperemesis gravidarum, and history of anxiety.

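### Secondary aim 6 names no statistic and no instrument able to show refractory CINV after dosing; the repeated MAT and FLIE data get no within-patient estimate

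*Combined protocol and SAP*

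**What the plan says.** The objective in Section 2.2 reads "To evaluate the occurrence of refractory CINV using CINV risk assessment at follow up day 7 compared to treatment day 1". The analysis in Section 9.3, item (6), is "The occurrence of refractory CINV will be analyzed using CINV risk assessment at follow up day 7 compared to treatment day 1". The synopsis repeats both, and nothing further is given. The opening sentence of 9.3 lists secondary outcomes (1) to (5) and leaves the sixth out.

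Refractory CINV is defined as a symptom state. Inclusion criterion 3 in Section 3.1 states "Must have refractory CINV defined as nausea and/or vomiting that occurs after the first cycle of cancer targeted therapy despite guideline-based prophylaxis", and the definition in Section 2.1 continues "and after first-line rescue medication with either a dopamine receptor antagonist, steroid, and/or benzodiazepine".

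Section 5.1 lists patient risk factors to be collected on Study Day 1 before dosing. They include "age, sex, alcohol consumption, history and severity of previous CINV, history of morning sickness with pregnancy, history of motion sickness", together with sleep and anxiety before chemotherapy. It cites published prediction models but selects none.

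On the MAT, footnote 8 of the Schedule of Events says "To be completed daily for 4 days after CINV prophylaxis or Akynzeo® dosing". Section 5.5.3 schedules the FLIE on the fifth day after prophylaxis, on Study Day 1, and on Day 5 of post-treatment observation. Items (3) and (4) of 9.3 summarise both instruments with one-sample proportions, means and confidence intervals.

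**The concern.** Aim 6 is worded as a before/after comparison of a symptom state, but the measure it names is a risk assessment. Predictors of CINV describe who is likely to have symptoms. They do not record who has them. An analyst following item (6) as written would have no outcome variable, no rule for calling refractory CINV present or absent on Day 7, and no summary measure.

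The data that could answer the question are already scheduled: the same patients complete the MAT and the FLIE before and after Akynzeo. The plan makes no use of that pairing, and it does not say which time point each one-sample summary describes. Section 5.3 makes this relevant: if feasibility is met, the team intends "analysis of secondary and exploratory objectives to determine if there are any trends towards a clinically-meaningful and plausible study endpoint". Two things are at stake: an interpretable result for aim 6, and a before/after estimate to inform the choice of that endpoint.

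**Working it through.** **1. The plan's own figure.** There is none for aim 6, the MAT or the FLIE. The only sample-size statement (Section 9.2: 50 patients, 70% against 85%, 80% power, Type I error 0.05) concerns the primary aim. With a one-sided normal approximation it reproduces: Φ[(0.15 − 1.645·√(0.70·0.30/50)) / √(0.85·0.15/50)] = Φ(0.86) = 80.5%. It has no bearing on this point.

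**2. Outcome against instrument.**

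| Needed for aim 6 | What the document gives |
|---|---|
| Outcome | A definition for entry (2.1, 3.1); no rule for Day 7 |
| Instrument | CINV risk assessment, undefined; the nearest text is the 5.1 list |
| Content of that list | Mostly fixed traits or pre-chemotherapy states; one item on previous CINV, with no recall window, score or threshold |
| Timing | 5.1 says Study Day 1; the schedule also marks the Day 4-7 column, and no footnote picks Day 7 |
| Statistic | None |

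Age, sex and a history of motion sickness will read the same on Day 7 as on Day 1 whether or not the patient is still vomiting.

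**3. Data collected against analysis planned.**

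| Instrument | Before dosing | After dosing | Analysis in 9.3 |
|---|---|---|---|
| MAT | Daily for 4 days after prophylaxis | Daily after Akynzeo | One-sample, no time point, no change |
| FLIE | Fifth day after prophylaxis; Study Day 1 | Day 5 | One-sample proportion impacted, no time point, no change |

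**4. What the existing data could deliver (illustration).** Assume equal pre and post SDs and correlation ρ. The 95% half-width of a paired mean change, in SD of the score, is t(0.975, n−1)·√(2(1−ρ)/n).

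| ρ | n = 50 (t = 2.010) | n = 35 (t = 2.032) |
|---|---|---|
| 0.3 | 2.010·√(1.4/50) = 0.336 | 2.032·√(1.4/35) = 0.406 |
| 0.5 | 2.010·√(1.0/50) = 0.284 | 2.032·√(1.0/35) = 0.344 |
| 0.7 | 2.010·√(0.6/50) = 0.220 | 2.032·√(0.6/35) = 0.266 |

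Here 35 is 70% of 50, used only as a lower assumption for complete pairs. The documents give neither the correlations nor the number of pairs.

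For a post-dose proportion, Wilson 95% intervals are 36.6% to 63.4% for 25/50 and 35.6% to 67.0% for 18/35. These show the precision of the proposed replacement measure, not the harm done by item (6).

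**5. Why a before/after test of presence is unsuitable.** Presence at baseline is about 100% by eligibility, so change can go only one way. With k of 50 patients no longer refractory and none newly so, the exact two-sided McNemar p-value is 2·0.5^k: 0.063 at k = 5 and 0.031 at k = 6. A significant result would need only 12% of patients to recover for any reason, including natural recovery.

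**The case against.** **The objectives do not ask for change.** The MAT objective is to characterise and the FLIE objective is to evaluate. One-sample summaries meet both in a single-arm trial whose primary aim is completion of procedures. This stands. A reader might infer that the plan contradicts itself by omitting a paired analysis; it does not. Section 5.3 is also conditional on feasibility and describes later exploration, so it creates no obligation.

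**Post-dose symptoms are already estimated.** Complete response (item 2) and the MAT yes/no items (item 3) carry confidence intervals. This stands in part. It would be wrong to infer that the trial learns nothing about symptoms after dosing, but neither item answers aim 6.

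**The 5.1 list may not be the intended instrument, and may not be exhaustive.** True. That leaves the instrument undefined rather than sound, and the single item on previous CINV cannot settle presence on Day 7.

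**The loss can be sized.** A reader might derive change from two separate means treated as independent, obtain half-widths of 0.40 SD (n = 50) and 0.48 SD (n = 35), and conclude that the plan is 1.2 to 1.8 times less precise than a paired analysis. The documents do not support this: the plan never makes that contrast, equal SDs are doubtful in patients selected for symptoms, and the planned FLIE outcome is binary.

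**Any nausea or vomiting on the MAT is not refractory CINV.** This stands. The definition also requires symptoms after rescue, so the replacement measure needs its own name and a rescue component.

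**The schedule marks the diary on Day 1 only.** A reader might infer that rescue use is unknown later. Section 5.5.1 answers this: the diary covers Study Days 1 to 7, and "This will include any rescue medications used to treat their CINV each day". Footnote 5 adds daily reminders.

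**Conclusion.** The point holds, in two parts of unequal weight. First, aim 6 as written yields no interpretable result: the instrument is undefined, its only candidate does not measure the outcome, and no statistic is named. This is more than missing detail, because filling in a statistic would not repair the mismatch. Second, the paired MAT and FLIE data are an unused opportunity, cheap to take up and in keeping with the before/after wording of aim 6.

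The weight is low to moderate: one secondary aim in a feasibility trial, with no effect on the primary conclusion. The size of the loss cannot be taken from the documents. The half-widths of 0.22 to 0.34 SD (50 pairs) and 0.27 to 0.41 SD (35 pairs) only show what a paired estimate could offer under assumed equal SDs and correlations of 0.3 to 0.7. Any change would be uncontrolled, so it should be read as description and not as evidence of drug effect.

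**What to change.** 1. **Redefine aim 6** in the synopsis, Section 2.2 and Section 9.3 as the proportion with nausea and/or vomiting on the MAT over a stated post-dose window. Report it overall and for patients who also used rescue medication in that window according to the diary, with a Wilson or exact 95% interval. Call the overall figure persistent CINV. Note that the diary form records dates, not clock times, so the order of rescue and symptoms within a day is not known. Do not test presence against baseline with McNemar. Keep the 5.1 risk factors as baseline predictors only.

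2. **Add descriptive paired changes with 95% intervals** for MAT vomiting, MAT nausea score, and FLIE total and domain scores. Use the post-prophylaxis MAT and the fifth-day FLIE as baseline. State the time point of every one-sample summary and how daily MAT forms become one value per window. Score episode count and nausea severity as 0 when the matching yes/no item is No. Those items are conditional, and blanks would otherwise drop responders from the complete pairs. Report the number of pairs, and label the changes as uncontrolled for regression to the mean and natural recovery.

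3. **Reconcile the timing rules:**
   - the MAT period (4 days in footnote 8; continuing daily through post-treatment observation in Section 5.5.2);
   - the FLIE day (footnote 4 against footnote 9, a difference of at most one day);
   - the MAT form's anchor, which is chemotherapy in Appendix 1 while Study Day 1 is the day of dosing. Written completion instructions can deal with this without altering the validated form.

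The cost is wording in the objectives, the footnotes and 9.3, completion instructions for the MAT, and a little more analysis. No new assessments are needed.

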#### **9.4 Data and Safety Collection and Monitoring**

All analyses will be conducted using the latest version of R (R Foundation for Statistical Computing, Vienna, Austria. <http://www.R-project.org/>) or SAS (SAS Institute, Cary, NC). The study team will provide support for data monitoring and cleaning.

Records and data to be obtained from the study subjects are detailed above in the Schedule of Events. Subject outcome information will be documented in the electronic medical record and subject's research record. Data for this study will be entered into a password-protected set of electronic case report forms via the Velos eResearch web-based system. Velos eResearch is an integrated software system for managing clinical trials. This system supports several clinical trial functions, including electronic case report forms, tracking and scheduling of subject visits and events, and study reporting. The software links to the UCSD Health System's Epic Electronic Medical Record System to provide improved information and integration for clinical research projects. A robust support team assists investigators in implementing protocols and calendars and building electronic case report forms. Velos provides automated data export procedures for designated users into Excel, and then transferred into SAS and R. Access to the Velos database for this study will be limited to those users required to perform study-specific functions such as data entry and monitoring. A designated study coordinator from the UCSD Moores Cancer Center Clinical Trials Office will be responsible for entering all study data.

In addition to adverse event monitoring and clinical oversight by the principal investigator and co-investigators, the clinical trials office internal monitor and/or a study team member will perform quality assurance of the study. Monitoring will occur once every 3-6 months based upon rate of subject enrollment.

This study will use the UCSD Moores Cancer Center Data Safety and Monitoring Board (DSMB) to provide oversight in the event that this treatment approach leads to unforeseen toxicities. It will be left to the Investigator's clinical judgment whether or not an adverse event is related and of sufficient severity to require the subject's removal from treatment. A subject may also voluntarily withdraw from treatment due to what he or she perceives as an intolerable adverse event.

If the subject was permanently withdrawn from the study or investigational product due to a serious adverse event, the Investigator will notify the IRB of serious adverse events occurring at the site and other adverse event reports received, in accordance with local procedures. Subsequent review of serious, unexpected and related adverse events by the PI, DSMB, IRB, and/or Helsinn may also result in suspension of further trial interventions/administration of study agent at a site. The PI and/or Helsinn retains the authority to suspend additional enrollment for the entire study as applicable. All serious adverse events must be reported within 1 working day of discovery or notification of the event. Serious adverse events will be collected

throughout the study period, beginning with the signing of the informed consent through study completion. For all collected AEs, the clinician who examines and evaluates the subject will determine the adverse event's causality based on temporal relationship and his/her clinical judgment. The degree of certainty about causality will be graded using the categories of definitely related, probably related, possibly related, unlikely and unrelated.

## 11.0 Appendices

---

### 11.1 Appendix 1- MASCC Antiemesis Tool

### MASCC Antiemesis Tool: Instructions

Your Name:

Date of Chemotherapy (this cycle):

			
Day	Month	Day	Day of the Week

Your Oncology Nurse:

Phone:

Your Oncology Physician:

Phone:

#### Information about this brief form:

The MASCC Antiemesis Tool (MAT) is a way to help your doctors and nurses be sure you get the best care there is to prevent nausea and vomiting from chemotherapy. By filling out this form, you can help us make sure that you are having the best control of these possible side effects. Here are the definitions used on this form:

**Vomiting:** The bringing up of stomach contents.

**Nausea:** The feeling that you might vomit.

Please answer all questions. There are no right or wrong answers, only your impression. If you have any concerns about how or when to complete this form, please ask!

Please notice that Question #4 and Question #8 have a different style. These questions are scales. For this type of question, just circle the number from 0 to 10 that most closely resembles your experience with your nausea and vomiting and write the number in the box to the right. An example of this form of question (but dealing with parking) is given below. Feel free to practice with this example or ask one of us to go over it with you.

How much difficulty did you have parking your car today?

0	1	2	3	4	5	6	7	8	9	10
None										
As much as possible										

(Write the number in this box)

Please return the form shortly after completing it, as discussed with us. Thank you!

MASCC Antiemesis Tool

Please fill this out the day after chemotherapy on:

Day  Month  Day of the Week

**Nausea and Vomiting  
during the first 24 hours after chemotherapy:**

(This page refers to the first 24 hours following chemotherapy):

1) In the 24 hours since chemotherapy, did you have any vomiting? Yes  No   
(Select one)

2) If you vomited in the 24 hours since chemotherapy, how many times did it happen?   
(Write the number of times in this box)

3) In the 24 hours since chemotherapy, did you have any nausea? Yes  No   
(Select one)

4) If you had nausea, please circle or enter the number that most closely resembles your experience.

How much nausea did you have in the last 24 hours?

0 1 2 3 4 5 6 7 8 9 10  
None As much as possible

(Write the number in this box)

